9.7.1 General considerations

Given between-country differences in the type of data used, governance regulations and patient privacy rules, and expected variations in the background risk of diseases, the countries will be analysed separately and combined in a meta-analysis (where the estimates for each country and cohort will be pooled, as applicable). The meta-analysis will be performed for the final report only. Any heterogeneity in results across the countries of study will be handled by using a random-effects model.

The distribution of continuous variables (age) will be examined graphically using boxplots, symmetry plots, normal quantile plots and normal probability plots. Exploratory analyses to provide insight into general patterns will be conducted using number and percent within each category with 95% confidence interval (CI) for categorical variables except cohort characteristics, and mean (standard deviation, SD), median (interquartile range, IQR), and other relevant summary statistics for continuous variables. Where appropriate, a log transformation of continuous variables (age) will be applied to handle skewness (back-

transformed prior to reporting) or a non-parametric approach will be adopted if there is no appropriate transformation. Quantitative variables may be categorised into quartiles as required.

Missing data for covariates will be described. Since missing values are expected to be few and distributed at random, in general, no replacement or imputation will be performed. Missing values will not be considered in the denominators for proportions.

The statistical analysis will be conducted using the SAS[®] software (version 9.3 or later) on Windows[™] (SAS Institute, North Carolina, US) or using R statistical program (version 3.5.0 or later).

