9.7.4 Meta-analyses

Assuming country-specific analyses have been completed, results for the analysis of primary and secondary outcomes that can be defined in all three countries can also be combined using a meta-analysis approach in order to achieve a more precise estimate of the observed measure of incidence rate and identify any potential country-specific patterns in the data. Incidence rates of the two different groups will be combined across the three databases. Because the current analysis will pool incidence proportions of sparse data, a logistic regression model with random intercept will be used to calculate the pooled the mean log odds, which will be back transformed to the probability scale to yield the median incidence proportion and 95% CI. A likelihood ratio test will be used to evaluate between-database heterogeneity. Database-specific incidence rates will be meta-analysed with a Poisson regression model with random intercept (25). The logarithm of the sum of patient-time at risk will be used as an offset variable to yield incidence rates per 1000 patient-years. Pooled incidence rates will be back-transformed from the logarithm scale to per 1000-patient-years unit.

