9.9.4 Data analysis

Despite adjusting the comparative analyses for several important potential confounders, residual confounding may remain. The data sources to be used do not include information on possible confounders related to disease status and severity, behaviour, lifestyle, family history or variation in healthcare delivery. Also, residual confounding may remain related to, for example, incomplete recording of diagnoses in the data sources.

Heterogeneity is anticipated in the meta-analyses combining the results from the three countries. Potential heterogeneity in the results from the countries will be addressed by using a random-effects model.

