10.5 Meta-analysis of incidence rate ratios

The results for incidence rate ratios (calculated according to secondary objective 7) will undergo a meta-analysis and be combined between the countries according to this section and illustrated in the tables (Table 61 to Table 65) and the figures (Figure 21 to Figure 30). The outcomes included in the meta-analysis are the primary objective, and for the secondary objectives 4, 5a, 5b, and 6.

The approach used is published by (Senn et al., 2011)

First the heterogeneity will be calculated and a p-value for the test if there is any heterogeneity will be calculated.

The formula used is computes I-square for the Q test for odds ratios as

 $I^2 = \max (100\% x (Q - (k - 1))/Q; 0)$

Where k is the number of strata and Q is a Q test for homogeneity of odds. This is implemented in the PROC FREQ procedure in SAS.

For interpreting I², (Higgins et al., 2003) suggest

 $I^2 = 0$ %, no heterogeneity, $I^2 = 25$ %, low heterogeneity, $I^2 = 50$ %, moderate heterogeneity, $I^2 = 75$ %, high heterogeneity. We should expect low heterogeneity.

A plot similar to the forest plot will be created for each of the outcomes showing the overall rate as illustrated in figure Figure 21. A Galbraith plot gives the same information as the forest plot, but

Ferring Pharmaceuticals

with another focus, where countries deviating from the mean are more easily detected as seen in Figure 21.

A funnel plot will be made. In a funnel plot should all points be in a triangle around the center vertical line as in Figure 22. If the parts of the triangle is missing, there could be a bias in the distribution or a classical bias in not publishing studies with negative results.

The sensitivity plot, in Figure 22, show the difference between a fixed model and a random model. The y-value for low values on the horizontal axis gives the value of a fixed model. In this figure the bold curve is decreasing indicating that the random effect is lower in absolute difference between treatments than the fixed effect model. It should be expected that a random model will have larger confidence intervals.

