An analysis of using a fixed effect or random effect model demands to have heterogeneity analyzed before judgements can be done and even with these analyses a precise determination can be difficult to make. If we are measuring the same effect a fixed effect model should be used. Otherwise, a random effect model should be used. If we were joining different studies from different countries with different outcome, we should use a random effect model. In this case we are measuring the same outcome, but in different countries and in different administrative systems and each country will have several administrative systems for the health care. Both random and fixed effect models analysis will be planned. An outcome table for the combined effect using both fixed effect models will be created showing the model type, the method, the estimated combined difference in treatment, the standard of the estimated combined difference together with upper and lower 95% CI of the estimated combined difference. An example is shown in Table 61.

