13 CHANGES FROM THE PROTOCOL

The statistical analysis are described in further details and explanatory figures have been added, compared with the outlines in the protocol.

The protocol states that 'Fatal and non-fatal MACE and VTE events will be assessed separately', but this is only possible in Denmark and Sweden. The SAP is updated.

The protocol stated that 'The length of the permissible gap will be varied (shortened or lengthened).', while the SAP specified 'The length of the permissible gap will be shortened'. Also the following has been added '. If two treatments with different ATC-codes are dispensed (or prescribed) on the same day only the treatment with the highest number of supplied days should be kept in the analysis.', since the previous formulation would give too long treatment periods.

Protocol stated in section 9.3.21 that 'If, recurrent events have been observed, a Cox model for recurrent events may be applied which will be detailed in the SAP.' The SAP specifies that this analysis will be presented if more than 5% of the patients has recurrent events.

Meta-analysis is in the protocol 'specified as random effect model', but the analysis has been expanded to both random and fixed effect model in the SAP and this is also reflected in the table shells.

Protocol stated that 'All adverse events/reactions collected for the study will be recorded and summarized in the interim *safety* analysis and in the final study report.' The SAP specifies that 'All adverse events/reactions collected for the study will be recorded and summarized in the interim analysis and in the final study report'. The word 'safety' was deleted since all statistical analysis will be presented in the yearly reports, except the meta-analysis.

The analysis of contraindications have been simplified and corrected compared with the protocol. Only one subpopulation for defining contraindications will be created, not the suggested 3 subpopulation, so that the extra medical conditions in secondary objective 5a, 5b, and 6 have been omitted, since it is not reasonable to have different contraindication at baseline for a possible future event. The usage of concomitant medical usage has also been omitted, since it is the condition at baseline that must determinate initiation of Nocdurna ® usage, not a future concomitant medical prescription, unknown to the prescribing physician at the index date.

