Phenothiazines with aliphatic sidechain, N05AA Chlorpromazine, N05AA01

Lithium, N05AN01

Antidepressants, N06A

Antiinflammatory agents, nonsteroids , M01A

Overactive bladder, G04BD

Benign prostatic hyperplasia, G04C

Desmopressin, H01BA02

Patients >= 65 years

Repeat all the above rows for this population

Incidence rate for	Nocdurna ®			LUTS				
	Denmark	Germany	Sweden	Overall	Denmark	Germany	Sweden	Overall
Diagnose code for low NA levels	XX (xx- xx)	XX (xx-xx)	XX (xx- xx)	XX (xx-xx)	XX (xx-xx)	XX (xx- xx)	XX (xx- xx)	XX (xx- xx)
All-cause mortality	XX (xx- xx)	XX (xx-xx)	XX (xx- xx)	XX (xx-xx)	XX (xx-xx)	XX (xx- xx)	XX (xx- xx)	XX (xx- xx)
Major cardiovascular events	XX (xx- xx)	XX (xx-xx)	XX (xx- xx)	XX (xx-xx)	XX (xx-xx)	XX (xx- xx)	XX (xx- xx)	XX (xx- xx)
Venous thromboembolic events	XX (xx- xx)	XX (xx-xx)	XX (xx- xx)	XX (xx-xx)	XX (xx-xx)	XX (xx- xx)	XX (xx- xx)	XX (xx- xx)
Congestive heart failure	XX (xx- xx)	XX (xx-xx)	XX (xx- xx)	XX (xx-xx)	XX (xx-xx)	XX (xx- xx)	XX (xx- xx)	XX (xx- xx)

Table 60. Meta-analysis. Incidence rates from the 3 countries and combined

Note: Incidence rate per 1000 person years are given together with 95% CI. SOURCE DOCUMENT: meta1.SAS GENERATED: 22:53:48 16JAN2021 DB version DEV: Simulated data, USERID: [name]

Figure 21. Meta-analysis. A Galbraith to the left and a forest plot to the right illustrating the difference between the countries for incidence rate ratio of symptomatic hyponatraemia.

[figure not shown]
[figure not shown]

Figure 22. Meta-analysis. A funnel plot to the left and a sensitivity plot to the right for incidence rate ratio of symptomatic hyponatraemia.

Trial Code: 000248

In the sensitivity plot the gap between the 95% CI dotted curves is increasing indicating that a random effect model will have a larger confidence interval.

Table 61. Meta-analysis of the combined effect using random and fixed model and 7 different
methods for incidence rate ratio of symptomatic hyponatraemia.

Model type	Method	Estimate	Standard Error	Lower CL	Upper CL
Fixed	Mantel Haenszel	Xx	Xx	Xx	XX
Fixed	Inverse variance weighting	Xx	Xx	Xx	XX
Fixed	Logistic regression	Xx	Xx	Xx	XX
Random	Der Simonian Laird	Xx	Xx	Xx	XX
Random	Hardy Thompson Wald	Xx	Xx	Xx	XX
Random	Hardy Thompson Profile			Xx	XX
Random	Normal Binomial mixture	Xx	Xx	Xx	XX

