Observe that the *fixed logistic regression in italic* is the model suggested in the protocol. SOURCE DOCUMENT: meta_fixed.SAS GENERATED: 22:53:48 16JAN2021 DB version DEV: Simulated data, USERID: [name]

Figure 23. Meta-analysis. A Galbraith to the left and a forest plot to the right illustrating the difference between the countries for all-cause mortality.

Figure 24. Meta-analysis. A funnel plot to the left and a sensitivity plot to the right for incidence rate ratio of all-cause mortality.

Table 62. Meta-analysis of the combined effect using random and fixed model and 7 different methods for incidence rate ratio of all-cause mortality

Figure 25. Meta-analysis. A Galbraith to the left and a forest plot to the right illustrating the difference between the countries for major cardiovascular events.

Figure 26. Meta-analysis. A funnel plot to the left and a sensitivity plot to the right for incidence rate ratio major cardiovascular events.

Table 63. Meta-analysis of the combined effect using random and fixed model and 7 different methods for incidence rate ratio of major cardiovascular events

Figure 27. Meta-analysis. A Galbraith to the left and a forest plot to the right illustrating the difference between the countries for venous thromboembolic events.

Figure 28. Meta-analysis. A funnel plot to the left and a sensitivity plot to the right for incidence rate ratio of venous thromboembolic events.

Table 64. Meta-analysis of the combined effect using random and fixed model and 7 different methods for incidence rate ratio of venous thromboembolic events

Figure 29. Meta-analysis. A Galbraith to the left and a forest plot to the right illustrating the difference between the countries for congestive heart failure.

Figure 30. Meta-analysis. A funnel plot to the left and a sensitivity plot to the right for incidence rate ratio of congestive heart failure.

[figure not shown]
Table 65. Meta-analysis of the combined effect using random and fixed model and 7 different methods for incidence rate ratio of congestive heart failure

Analysis of several events for each patient (Optional)

Table 66. Optional. Incidence of symptomatic hyponatraemia in country, if there are more than 5% of the patients that are having more than 1 event

Repeat Table 9, but with a changed regression taking into account that there are several events for more than 5% of the patients. The SAS macro must be re-programmed.

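### The Table 61 footnote names the fixed-effect logistic row as the protocol's meta-analysis model, but the protocol specifies random effects and the SAP names no pooled IRR as the result

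*Protocol*

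**What the plan says.** **Protocol.** Section 9.7.1 sets the general rule: "Any heterogeneity in results across the countries of study will be handled by using a random-effects model". Section 9.9.4 adds that "Heterogeneity is anticipated in the meta-analyses combining the results from the three countries" and gives the same remedy. Section 9.7.4 is more specific. For incidence proportions, "a logistic regression model with random intercept will be used to calculate the pooled the mean log odds". For incidence rates it uses a Poisson model, also with a random intercept. Both models in 9.7.4 pool the two groups' proportions and rates, not the ratio between groups.

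**SAP.** Section 13 describes the protocol's meta-analysis as a random-effects model and says that "the analysis has been expanded to both random and fixed effect model in the SAP". Section 10.5 plans both model types for the IRRs. Table 61, whose title begins "Meta-analysis of the combined effect using random and fixed model and 7 different", has three rows typed Fixed (Mantel-Haenszel, inverse variance, logistic regression) and four typed Random (DerSimonian-Laird, Hardy-Thompson Wald, Hardy-Thompson profile, normal-binomial mixture). The footnote under the table singles out the fixed logistic regression, set in italics, and says that it "is the model suggested in the protocol".

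**The concern.** A table with seven pooled answers to one question needs a statement of which answer counts. Section 10.5 gives none. The footnote then marks one row as the protocol's own, and a reader of the final report will reasonably take that row as the pre-specified analysis.

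The row is a fixed-effect one. Its standard error assumes a single common ratio in Denmark, Germany and Sweden and carries no between-country component. If the ratios differ, the interval presented with protocol status is too narrow for the average effect. Pooled IRRs are planned for symptomatic hyponatraemia, all-cause mortality, MACE, VTE and exacerbation of heart failure. In a post-authorisation safety study, an estimate should not be presented as protocol-specified when it is not.

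**Working it through.** **Step 1. Set the texts side by side.**

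| Place | Model attributed to the protocol |
|---|---|
| Protocol 9.7.1 | random effects |
| Protocol 9.7.4, proportions | logistic, random intercept |
| Protocol 9.7.4, rates | Poisson, random intercept |
| Protocol 9.9.4 | random effects |
| SAP 13 | random effects; fixed added by the SAP |
| SAP 14, Table 61 footnote | fixed logistic regression |

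The footnote stands alone against three protocol sections and the SAP's own change list. No protocol section suggests a fixed-effect logistic model.

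**Step 2. Is any row of Table 61 literally the protocol's model?** No. The logistic model of 9.7.4 pools proportions within a group. Its random intercept lets the level of risk vary by country but does not let a treatment ratio vary. The random-effects basis for pooled ratios therefore comes from 9.7.1 and 9.9.4.

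**Step 3. How much does the label matter?** The documents give no figure to reproduce, so this is an illustration.

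*Inputs.* Planned NOCDURNA patients n = 2650, 2610 and 1830 (protocol 9.5.3; SAP 3.1.2). I² takes the benchmark values listed in SAP 10.5.

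*Assumptions.* The variance of each country's log IRR is proportional to 1/n: equal event rate and follow-up per patient, and a LUTS cohort so large that its contribution is negligible. The inverse-variance estimate stands in for the fixed logistic row.

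*Formulas*, with weights w = n up to a common factor that cancels:
- W = Σw and C = W − Σw²/W
- Q = 2/(1 − I²) and τ² = (Q − 2)/C
- fixed-effect variance = 1/W
- true variance of the fixed-effect estimate = 1/W + τ²·Σw²/W²
- random-effects variance = 1/Σ[1/(1/w + τ²)]
- coverage of the fixed interval = 2Φ(1.96·√(fixed variance/true variance)) − 1

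*Numbers.* W = 7090, Σw² = 17,183,500, C = 7090 − 2423.6 = 4666.4, Σw²/W² = 0.3418.

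At I² = 50%: Q = 4 and τ² = 2/4666.4 = 0.0004286. The true variance is 0.0001410 + 0.0004286 × 0.3418 = 0.0002875. The square root of 0.0001410/0.0002875 is 0.700, and 1.96 × 0.700 = 1.373, so coverage is 83%.

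| I² (assumed) | Random/fixed interval width, log scale | Coverage of nominal 95% fixed interval |
|---|---|---|
| 0% | 1.00 | 95% |
| 25% | 1.16 | 91% |
| 50% | 1.42 | 83% |
| 75% | 2.02 | 67% |

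With equal country variances the width ratio is 1/√(1 − I²), giving 1.155, 1.414 and 2.0 at 25%, 50% and 75%. The country weights hardly matter.

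**Step 4. Could the heterogeneity statistics settle the choice?** With three equal-variance countries, Q is distributed as χ² on 2 degrees of freedom divided by (1 − I²). At a true I² of 50%:
- P(Q < 5.99) = 1 − exp(−5.99 × 0.5/2) = 0.78, so the test misses the heterogeneity 78% of the time.
- P(Q < 2), where estimated I² is exactly 0, is 1 − exp(−0.5) = 0.39.

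Three countries are too few for Q or I² to choose the model.

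**The case against.** The strongest reply is that this is a one-line documentation slip. The footnote says which model the protocol suggested, not which row is the conclusion. SAP 13 describes the protocol correctly, and the four random-effects rows are reported whatever Q or I² shows. The objectives are descriptive, p-values are descriptive (SAP 3.1.2), and Table 61 has no p-value column. If I² is estimated as 0, the DerSimonian-Laird and inverse-variance intervals coincide. All of this stands, and it limits the consequence to the label and to the absence of a named result.

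Several stronger readings are tempting but not supported:

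- *That the SAP lets a heterogeneity test choose the model.* Section 10.5 does say "An analysis of using a fixed effect or random effect model demands to have heterogeneity analyzed before judgements can be done", but the sentence goes on to concede that a precise determination may still be difficult, and the paragraph then plans both model types. There is no test-based rule.
- *That "We should expect low heterogeneity" contradicts protocol 9.9.4.* The protocol gives no size. SAP 10.5 calls I² = 25% low, which is not none, and the sentence concerns ratios. The comment after Table 5 in SAP 10.3 explains why ratios may be more alike across countries than rates.
- *That the fixed row would falsely exclude 1 in a quarter to a half of cases.* Rejection rates of 24% to 52% can be produced, but they need assumed event counts and between-country SDs of 0.2 to 0.3, equivalent to I² of roughly 64% or more. The documents give neither quantity.
- *That the footnote governs Tables 62 to 65.* Only their titles are given. They repeat the seven-methods wording, so a shared layout is likely but inferred.

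**Conclusion.** The footnote is wrong and should be corrected. The error is more than clerical because SAP 10.5 leaves seven pooled IRRs unranked, and the footnote gives protocol status to one whose interval omits between-country variation. The size depends on heterogeneity that is not yet known: nothing is lost at I² = 0, coverage is about 91% at 25% and about 83% at 50%, under the equal-rate and large-comparator assumptions above. The documents do not support saying that the fixed row is the declared headline result, that random-effects results are suppressed, or that a stated false-positive rate will occur.

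**What to change.** Before the final report:

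1. Reword the Table 61 footnote so that no fixed-effect row is called the protocol's model. It should say that protocol 9.7.1 and 9.9.4 specify random effects and that the fixed-effect rows were added in the SAP.
2. Name one random-effects analysis that supplies both an estimate and an interval as the protocol-consistent pooled IRR for Table 61 and, if they share its layout, Tables 62 to 65. The Hardy-Thompson profile row cannot serve alone, because the shell leaves its estimate and standard error blank. The Hardy-Thompson estimate with its profile-likelihood limits would do, as would another random-effects row.
3. Label the three fixed-effect rows as sensitivity analyses.
4. State that this choice does not depend on Q or I² from three countries.

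The sentence expecting low heterogeneity need not be deleted. The cost is SAP wording only, since the random-effects rows are already planned. The interval presented as the protocol-consistent result may be wider.

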16 APPENDICES

16.1 SAS macros

Two SAS macros will to do the main part of the analysis

A SAS macro has been developed to be used in the main part of the analysis have been develop. The macro is called NOCDURNA_MAC. There are several reasons for this approach.

- 1) It saves overall time used in the program development.
- 2) The Poisson regression in SAS is not doing any back transformation from the log transformation of the rates, so it is nice to have that done already.
- 3) It is expected that there will be differences in the rates between the different countries and when a common macro have been used, these differences must be found in other places than in the statistical analysis
- 4) The QC is simplified, since a potential error in the macro will be found/tested by at least 3 different persons. If an error/improvement is found the project manager and project statistician should be notified.
- 5) Less work for the statistician and more work for the programming teams.

The macro is performing the main Poisson regression for rate calculation as specified in the SAP, and this macro should be used in the primary objective, and the secondary objectives 2, 3, 4, 5a, 5b, 6, 8, and 9. Secondary objective 9 will need minor output corrections, but the main part of the analysis can be done by the NOCDURNA_MAC macro.

The overall principle in developing the macro has been to keep the SAS programming simple and easy to understand. Shortcuts to make the output elegant has been avoided. Also the listing has not been turned off, so the LOG-file can be inspected. There are no loops for resetting or testing if the input is valid, and there are no clean-up for deleting datasets that have been used during the macro

Runtime error might be expected where there are zero events and where the Poisson model cannot converge, but an early graphical output inside the macro should be able to find these cases and during test runs with zero events the macro has executed without errors. If the Poisson regression is unable to converge, the mean unadjusted events rates will be used in the interpretation of the results.

The macro call is

%NOCDURNA_MAC(baseline=baseline, eventdata=eventdata
compare=compare,out_table=out_table,dir=dir,ttitle=ttitle);

The overall idea is to create two datasets, one with all patients and their characteristics, and another dataset with all events and the characteristics of the events. The macro will write to a word compatible file (a RFT - file) and the output place of the file and the title of the generated table must be specified in the macro call.

Figure 32. Data flow in the SAS macros for Poisson regression.

[figure not shown]

Table 67. Description of the input datasets. The baseline dataset must contain only one observation
for each patient

Variable	Туре	Length	Description
Patent_id	Num	8	A unique value for each patient
Class	Char	9	LUTS or NOCDURNA, LUTS can be changed to a variable in secondary objective 9.
gender	Char	1	Gender, F or M
exposure	Num	8	Length of exposure time in study, from index date to end of study, in days

Log_exposure Age_class	Num Num	8 12	Natural log function of exposure in log(days) Age classified in '<65 years ', '65-74 years' and
			'>=75 years '. Don't forget the space/blank in front of
			'B<65 years ' to get the right sorting

Below is a partial listing of the dataset

Obs	class	age_class	gender	exposure	log_ exposure	patient_ id
3025 3026 3027 3028	NOCDURNA LUTS NOCDURNA LUTS	>=75 years 65-74 years 65-74 years <65 years	F F M	44.3876 36.8901 50.8905 80.8589	3.79296 3.60794 3.92968 4.39271	3025 3026 3027 3028

The events dataset must have one observation for each event. Each patient can have several observations if the patient has several events. An unlimited number of events are possible for each patient. There are 3 variables in the Eventdata dataset

Table 68. Description of the input Eventdata. There can be several events for each patient

Variable	Туре	Length	Description
Patent_id	Num	8	A unique value for each patient
Time_to_event	Num	8	Time in days between index date and date of event
Event_one	Num	1	Equal to one when there is an event, useful in further calculation.

Below is a partial listing of the dataset

Obs	patient_	TIME_TO_	event_
	id	EVENT	one
37 38 39 40 41	318 318 355 364 367	38.993 83.672 57.820 1.000 81.453	1 1 1

Please observe that the patient with $patient_id = 318$ has 2 events, one after 38 days and another after 83 days. The decimals in the variable time to event is due to the synthetic nature of the data.

There are 3 variables to specify the output for the macro, one for the table, one for the directory and one for the table and figure title.

The SAS macro was:

%NOCDURNA_MAC(baseline=baseline,eventdata=eventdata,compare=LUTS,out_table=out_tabl e,dir=dir,ttitle=ttitle);

The 'LUTS' value in the macro can be changed to e.g. 'Off label' when objective 9 is analysed. Please check that the columns are in the correct order in the output and not interchanged.

The SAS macro variable 'DIR' gives a reference to the directory where the RTF table is written, in the development case, the 'C:\temp' directory have been specified, but each site will have a designated directory for the output. Please observe that there is no ending '\' in this macro variable.

The last SAS macro variable 'TTITLE' gives both the headline of the table and the headline (title) of the figure generated inside the SAS macro. Please do not use any ',' inside the text string specified in the macro call.

That is all for the input datasets.

Calculations inside the macro.

The Poisson regression is performed and a calculation is used to calculate the yearly rates. This is the key analysis.

```
ods output ParameterEstimates=ParameterEstimates;
proc genmod data=to_poisson;
class class gender age_class;
model events = class age_class gender / dist=poisson link=log
offset=log_exposure scale=d type3;
store p1;
run;
ods output lsmeans=lsmeans;
proc plm source = p1;
  lsmeans class /ilink cl;
run;
quit;
```

The 'STORE P1' is generating data that can be used for post analysis calculations, in this case will the 'PROC PLM' use the 'P1' data collection.

After the yearly rate per 1000 patient years are calculated and merged together with the rest of the analysis and a 'PROC REPORT' is used for writing the output RTF file.

When the macro is run several time, be sure to exit the Word document between different runs of the SAS macro, if not the output file will be locked and SAS will not be able to write to the file.

